### 9.4.2 ANALYSIS OF THE PRIMARY ENDPOINT(S)

- Specific Aim 1, Primary Endpoint

Our primary outcome is family member symptoms of depression over the 6-months post-randomization period. We will follow the intention-to-treat principle. Our primary analysis will use a linear mixed effects model with family member symptoms at all time points (1,3,6 months) as the response, main effects for intervention and time points, and a random effect to account for multiple measurements (time points) per family member. Given multiple family members per patient, we will also include a random effect for family. Time point is included as a factor variable to allow for nonlinear effects. We will also adjust for site, since randomization is stratified by site, and consider adjustment for response (symptoms of depression for primary outcome) at baseline (randomization). This model allows the average response to be different at 1, 3, and 6 months, but assumes the intervention has the same effect at each of these times. The secondary analysis allows the effect of intervention to be different across time by including an interaction between time and intervention. The advantage of using the data at all three time points and

a mixed model approach is that we can gain precision; it also allows for missing responses, assuming the responses are missing at random. We will use a similar approach for the other continuous family and patient outcomes, and a generalized linear mixed effects model for the binary outcome of goal-concordant care. As a sensitivity analysis, we will consider models including only one family member per patient, chosen randomly.

---

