### 6.3 MEASURES TO MINIMIZE BIAS: RANDOMIZATION AND BLINDING

The unit of randomization is the patient. The potential for contamination is minimized because the focus of the intervention is specific to the individual patient and family and tailored to their needs. Randomization will occur in variable-sized blocks stratified by site. Family will be clustered under patients.

The intervention precludes blinding clinicians, patients, or family to treatment group. However, we will blind study staff involved in data collection to group assignment via surveys send and completed by mail and online. A number of the outcomes could theoretically allow the introduction of bias if patients or family in the intervention arm give different ratings for reasons other than the intervention (i.e., to please researchers). Therefore, we will not highlight the primary outcome during the consent process, and all participants will receive contact with study staff for completion of study materials which will help mitigate this potential source of bias.

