## 8 STUDY ASSESSMENTS AND PROCEDURES

### 8.1 ENDPOINT AND OTHER NON-SAFETY ASSESSMENTS

*Pre-Screening:* automated lists of consecutive patients admit to participating ICU services are generated using ICD10 codes and calculated APACHE II scores to narrow assessment of eligibility; time frame is within 48 hours of ICU admission; existing information from the patient's EHR will be accessed, obtained and kept as study data under a waiver of HIPAA authorization.

*Screening:* study staff manually screen patient electronic health records to confirm eligibility using established inclusion and exclusion criteria; time frame is 10-14 days from eligibility.

*Recruitment:* study staff contact eligible patient, LNOKs, family members to inform them about the study and ascertain if they are interested and able to participate; time frame is 10-14 days from eligibility.

*Enrollment:* subjects complete informed consent procedures with study staff and are given baseline questionnaires to complete (in person, by mail, by telephone, or online); time frame is 10-14 days from eligibility, however additional family members may be enrolled after this period until 1-month from patient randomization.

*Randomization:* subjects are randomized when a family member's completed baseline questionnaire has been received by the study; time frame is within 1 business day from receipt.

*Intervention:* a communication facilitator (study nurse/interventionist) makes contact with the enrolled subject within 1 business day from randomization; duration of intervention is 3 months, however this may be shorter if the patient dies, or extended if the facilitator finds a need to do so based on her clinical judgement; facilitators have a final contact with participants at the end of the period.

*Control:* subjects are contacted by study staff as the patient's hospital trajectory is monitored; time frame for check-in contacts is at transition out of ICU/to acute care, discharge from hospital, and in the event of patient death (condolence card).

*Follow-up at 1-month:* subjects are contacted by study staff and reminded of the first follow-up questionnaire at 1 month after randomization; reminders are sent at two weeks if questionnaires have not been returned; subjects may also be reminded by phone, email, text for six weeks (one contact per week).

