## 9.2 SAMPLE SIZE DETERMINATION

The primary focus for sample size estimation is the primary outcome: mean family member depression over 6 months as assessed by the HADS depression subscale. For all calculations, we assume a two-sided test with a significance level of 0.05. If we assume 300 total family members (1 family member per patient and 150 per arm), a standard deviation of HADS depression scores of 4.2 points in both arms, 3 measurements of depression (at 1,3, and 6 months), and an intraclass correlation (ICC) of 0.2, we will be able to detect a difference in mean depression of at least 0.93 points with 80% power and 1.07 points with 90% power (Power Table Below). These detectable differences at 80% power become 0.86 if the ICC is 0.1 and 1.05 if the ICC is as high as 0.4. If we had only 1 measurement instead of 3 per family member or, equivalently, if the ICC were 1, we would have 80% power to detect a difference of at least 1.36 points. Across all of these varying conditions, detectable differences are slightly within or below estimates of the minimally clinically important difference (MCID) of 1.6 to 2.0 available from the literature, suggesting we will have adequate power to identify a minimally clinically important difference. Although these MCIDs and minimum detectable effects are just estimates, they provide the best available evidence that power will be adequate to detect relatively small but important differences. We anticipate >80% complete data for all outcomes so we will randomize 376 patients to achieve 300 patients and at least 300 family members with complete data. If our response rate is 70%, then we would expect responses for 263 patients and at least 263 family members and with an ICC of 0.2, we would be able to detect a difference in mean depression of at least 0.99 points with 80% power. If we have more than 1 family member per patient (1.5 is expected), we will be able to detect smaller differences at the same power. In addition, we have 80-90% power to detect reasonable effects for other continuous outcomes in Aim 1. For the binary outcome of goal-concordance care, we have about 80% power to detect a difference in proportion concordant of 0.6 and 0.7, with 3 measurements from each of 300 total participants and an ICC of 0.13; the estimate of 0.6 for the controls is from a prior study and our preliminary data. We targeted power to identify differences within or slightly less than available estimates of “minimally important clinical differences” so that we would be confident that we would be powered to detect a minimally important clinical difference.

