## 9.4 STATISTICAL ANALYSES

### 9.4.1 GENERAL APPROACH

Our primary analysis approach involves mixed effects models. This likelihood-based approach assumes that missing data (responses) are missing at random. However, this assumption may not hold, so further sensitivity analysis is necessary. Multiple imputation using MICE will be performed to address missing data. Missing values will be imputed based on patient characteristics (minority race, age and having three or more chronic diagnoses), family characteristics (age, education, employment, self-reported health status and financial situation) and outcomes from previous time points. Twenty imputations will be performed, and final results will be pooled. The multiple imputation approach will be useful for our sensitivity analyses which include adjustment for covariates, some of which may be missing for some participants.

We will also perform sensitivity analyses regarding handling of missing data and enrollment characteristics of participants. We will consider different approaches and summarize any similarities and differences in results or conclusions from these approaches.

Our goal will be to minimize missing data through minimizing respondent burden, offering multiple methods for survey completion, and having trained staff with repeated contact with participants. However, data could still be missing due to skipping individual items on a survey, omissions in EHR, lack of follow-up, or death. We will quantify the amount of missing data, evaluate associations with participant characteristics, and minimize bias by applying appropriate methods to account for missing data.

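### The primary model leaves adjustment for baseline HADS-D undecided, and no rule covers baseline scores completed after randomisation or left incomplete

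*Combined protocol and SAP*

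**What the plan says.** Section 9.4.2 describes a linear mixed model for HADS-D at 1, 3 and 6 months, with "main effects for intervention and time points, and a random effect to account for multiple measurements (time points) per family member". A random effect for family and adjustment for site are also firm commitments. Baseline HADS-D is not: the text says the team will "consider adjustment for response (symptoms of depression for primary outcome) at baseline (randomization". The section gives no criterion, default or deadline, and applies a similar approach to the other continuous outcomes.

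On the timing of baseline:

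- Section 4.1 places randomisation after the baseline questionnaire, and the questionnaire before the facilitator becomes involved. HADS is on the list for the initial survey.
- Section 8.1 defines enrolment as the point where "subjects complete informed consent procedures with study staff and are given baseline questionnaires to complete", and then "subjects are randomized when a family member's completed baseline questionnaire has been received by the study".
- Section 8.1 also says "additional family members may be enrolled after this period until 1-month from patient randomization".
- Section 5.4 withdraws family members who do not complete the baseline questionnaire.
- Section 6.3 states: "The intervention precludes blinding clinicians, patients, or family to treatment group".

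Section 9.4.1 accepts that "data could still be missing due to skipping individual items on a survey". It plans multiple imputation with 20 imputations and links it to covariate-adjusted sensitivity analyses. It does not name baseline HADS-D.

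**The concern.** There are two linked gaps.

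The first is model choice. With the baseline term optional, the primary result could be reported with or without it, and both versions fit the text. Either is valid if fixed in advance. A choice made after both results are known would not hold the 5% level. Leaving baseline out also gives up precision from data the trial already collects.

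The second is which score counts as baseline. The patient is randomised when one relative's questionnaire arrives. Another relative may enrol up to a month later. By then the facilitator may have been in contact with the family for weeks, since section 8.1 sets first contact within one business day of randomisation and section 4.1 sets daily contact in the ICU. A HADS-D score completed then is a post-randomisation measurement in an unblinded family. Adjusting for it could remove part of the intervention effect or otherwise bias the estimate. The plan does not say whether such a score would be used.

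**Working it through.** **Inputs from section 9.2:** two-sided alpha 0.05; 300 family members, one per patient, 150 per arm; SD 4.2; three measurements; ICC 0.2 (also 0.1 and 0.4); 263 family members at 70% response.

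**Assumption:** the correlation r between baseline HADS-D and each follow-up score. The documents do not give it, so a range is shown.

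**Step 1: reproduce the plan's figures without a baseline term.** The variance factor for the mean of three follow-ups is v0 = (1 + 2 × ICC)/3. The detectable difference is (1.960 + 0.842) × 4.2 × sqrt(2/150 × v0). At ICC 0.2, v0 = 0.4667 and the result is 0.928. The plan says "we will be able to detect a difference in mean depression of at least 0.93 points with 80% power".

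| Setting | Stated | Recomputed |
|---|---|---|
| ICC 0.2, 80% power | 0.93 | 0.928 |
| ICC 0.2, 90% power | 1.07 | 1.074 |
| ICC 0.1, 80% power | 0.86 | 0.859 |
| ICC 0.4, 80% power | 1.05 | 1.052 |
| One measurement, 80% power | 1.36 | 1.359 |
| 263 family members, ICC 0.2, 80% power | 0.99 | 0.991 |

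The sample size therefore matches the model without baseline adjustment.

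**Step 2: add baseline.** Adjustment lowers the variance factor to v1 = v0 − r². At ICC 0.2 with 150 per arm:

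| r | v1 | Detectable difference, 80% power | Power at 0.928 | Equivalent extra family members, 300 × (v0/v1 − 1) |
|---|---|---|---|---|
| none | 0.4667 | 0.93 | 80% | 0 |
| 0.2 | 0.4267 | 0.89 | 83% | 28 |
| 0.3 | 0.3767 | 0.83 | 88% | 72 |
| 0.4 | 0.3067 | 0.75 | 93% | 157 |

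At r = 0.1 the gain is slight (0.92). At ICC 0.4 the difference falls from 1.05 to 0.90 (r = 0.4) or 0.80 (r = 0.5).

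**Step 3: what selection between the models would cost.** Under the null, the two test statistics have correlation sqrt(v1/v0). At ICC 0.2 this is 0.956, 0.898 and 0.811 for r = 0.2, 0.3 and 0.4. The chance that at least one exceeds 1.96 in absolute value, from 4 million simulated pairs, is 6.4%, 7.0% and 7.7%. At ICC 0.4 and r = 0.5 it is 8.0%. These figures apply only if both models are run and the smaller p-value is always reported.

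**Step 4: which baseline scores are secure.** Taken together, sections 4.1, 8.1 and 9.4.2 put baseline before randomisation for the relative whose questionnaire triggers it. With one relative per patient, as in the sizing above, every baseline score is therefore pre-randomisation. The gap opens only for additional relatives, whom the plan does expect: 564 family members for 376 patients is 1.5 per patient. Section 5.4 removes relatives with no baseline questionnaire at all. What remains without a rule is late scores and skipped HADS-D items.

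**The case against.** The best defence is that the plan does give a steer. Section 9.4.1 places covariate adjustment among the sensitivity analyses, and the calculations in 9.2 contain no baseline term. On that reading the primary model adjusts for site only. The same section plans multiple imputation for missing data and sensitivity analyses on participants' enrolment characteristics, which could cover late enrolment. This has some force, but it does not settle the matter. Section 9.4.2 puts the baseline term inside the description of the primary model, and 9.4.1 neither names baseline HADS-D nor says what to do with a score completed after randomisation.

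Four stronger readings are tempting and should be resisted.

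- A reader might infer that baseline has no definition. It has one for the relative whose questionnaire triggers randomisation, and section 5.4 deals with wholly absent questionnaires.
- A reader might infer that the trial is underpowered. It is not on this account: the stated figures reproduce without adjustment, and adjustment can only help.
- A reader might infer that the model will be picked on its p-value. No section says so.
- A reader might take the 188 relatives beyond one per patient (564 − 376) as the number of late scores. Nothing says those relatives enrol late, and the share cannot be combined with a sizing that assumes one relative per patient.

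**Conclusion.** The point holds as a free improvement, not as an error that invalidates the design. The baseline term in the primary model is undecided, and post-randomisation or incomplete baseline scores have no handling rule.

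The size of the gain depends on a correlation that the documents do not give. At ICC 0.2 and correlations of 0.2 to 0.4, the 80%-power detectable difference falls from 0.93 to between 0.89 and 0.75, so the gain ranges from small to substantial. The matching type I error of 6.4% to 7.7% is what consistent selection of the smaller p-value would produce under those assumptions. It is neither a forecast nor an upper limit over all correlations. All these figures take one relative per patient, complete baseline scores and equal correlation of baseline with each follow-up.

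The late-score bias is conditional: it arises only if such scores are used as baseline. The documents do not allow its size to be estimated.

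**What to change.** Before any unblinded outcome analysis, amend section 9.4.2 as follows.

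1. State that the primary model adjusts for baseline HADS-D, and report the model without it as a sensitivity analysis.
2. Accept as baseline only a HADS-D completed on or before the patient's randomisation date, judged by the questionnaire's completion date.
3. Treat later or incomplete scores as missing, and fill them by one stated rule that keeps every family member in the model. Either a fill computed without arm or follow-up data, or the multiple imputation already planned in 9.4.1, would serve.
4. Add a sensitivity analysis limited to relatives with a true pre-randomisation score.
5. Apply the same rule to continuous secondary outcomes measured at baseline, such as HADS-A.

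The cost is three or four sentences, a check of completion dates against randomisation dates, and two extra sensitivity models. No new data collection is needed.

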Post-traumatic stress (civilian)	Subjective distress caused by a traumatic event assessed with the Impact of Event Scale-6 (IES-6).	The IES-6 uses 6 self-report items to assess subjective distress caused by a traumatic event. Items are rated on a 5-point scale ranging from 0 ("not at all") to 4 ("extremely").
Family experience of quality of life at the end of life for patients with serious illness	Measure of family experience of patients with serious illness using the QUAL-E (Fam). Outcomes will be focused three of the instrument's subscales: Relationship to Healthcare Providers, Sense of Completion, and Preparation Issues	The QUAL-E (Fam) is a validated ~17-item companion instrument to the patient QUAL-E measure of quality of life at the end of life.
Healthcare Costs and Utilization	Index hospitalization length of stay; subsequent hospitalization and ICU admissions; palliative care consults; outpatient visits/Emergency Department visits (as available).	We will measure hospital readmission after initial hospital discharge through the electronic health record (EHR), institutional billing systems and, patient/family self-reports. All hospitals are in one system facilitating data collection. By using all three sources for data, we will capture hospitalizations regardless of healthcare system. Our primary focus will be readmission within 30 days as this is a national standard, but we will also collect data from the EHR and from patient/family interviews to record all readmissions, emergency department visits, clinic visits, inpatient and outpatient palliative care consults, and home care over 6 months. All occasions of healthcare use will be confirmed through chart review and valued using the

OBJECTIVES	ENDPOINTS	JUSTIFICATION FOR ENDPOINTS
		Medical Expenditure Panel Survey and the Healthcare Cost and Utilization project, with additional information from Institutional financial systems will be used to capture costs of care rather than charges.
Tertiary/Exploratory		
Key Implementation Factors	Factors include: aspects of the intervention, inner and outer settings, individuals, and processes of care.	Qualitative interviews after individual participation. Interviews will be guided by the Consolidated Framework for Implementation Research (CFIR) to explore the factors associated with implementation. Individual constructs within these domains were chosen to fit this specific intervention and context.

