**Intervention Fidelity:** We will record type (mode), frequency and duration of all facilitator contacts for each patient and family so that we will have this information to assess intervention fidelity as well as “dose.” We will also ask participants for permission to periodically audio-record their visits with the interventionist. This procedure will assist in monitoring and maintaining intervention delivery. De-identified transcripts may also be used for training future interventionists.

**Outcome Assessment:** Both intervention and control subjects will be asked to complete questionnaires. At baseline/enrollment, prior to the facilitator’s involvement, both intervention and control group subjects will meet or confer with the research staff who will distribute initial questionnaires. The questionnaires will be self-administered, although study staff will be available to provide assistance. The study staff member collecting the baseline questionnaires will be able to notify the subjects about their randomization status at that time.

Chart abstraction of patient data from EHR will include: age, sex/gender, Race, Ethnicity, primary diagnosis, secondary diagnoses and comorbidities, admission dates (e.g. hospital, ICU, acute care) , discharge dates (e.g. hospital, ICU, acute care), processes of care (e.g. care planning, transitions) , treatment intensity (e.g. receipt of CPR, use of mechanical ventilation), Referrals/Consults (e.g. palliative care) , data required to calculate APACHE II scores (e.g. lab values, Glasgow Coma Scale, medication dosage), outpatient healthcare utilization: number, type and dates of primary and specialty care visits, and date of death. Dates of death will also be collected from publicly available death certificate data.

Family questionnaires will be completed at baseline, 1-month, 3-months, and 6-months post randomization. Questionnaires will contain measures including:

- Relationship Scales Questionnaire (RSQ) – initial survey
- Hospital Anxiety and Depression Scale (HADS) – initial and follow-up surveys

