- Concordance between the care patients want and the care they are receiving will be measured with two questions from the SUPPORT study. The first defines patients’ preferences: “If the patient had to make a choice at this time, would the patient prefer a course of treatment focused on extending life as much as possible, even if it means having more pain and discomfort, or would the patient want a plan of care focused on relieving pain and discomfort as much as possible, even if that means not living as long?” The second question assesses perceptions of current treatment using the same two options. The outcome is a dichotomous variable of whether the preference matches the report of care received. Although this creates a “false dichotomy” in that many patients want both, this forced choice helps identify patients’ top priority. – initial and follow-up surveys
- Single-Item health status question (SF-1): “In general, would you say your health is: Excellent, Very good, Good, Fair, Poor” – initial survey and follow-up surveys
- Single-Item health status question (SF-1): “In general, would you say your family member/friend’s health is: Excellent, Very good, Good, Fair, Poor” – initial survey and follow-up surveys (proxy for patient)
- FRAIL scale (Fatigue, Resistance, Ambulation, Illnesses, & Loss of Weight) – initial survey and follow-up surveys (proxy for patient)
- Preferred Role in Decision-Making – initial survey and follow-up surveys
- Perceived Competence Scale (PCS) – initial and follow-up surveys
- Impact Of Events Scale-Revised (IES-6) – follow-up surveys
- Measuring the Quality of Life of Seriously Ill Patients (QUAL-E FAMILY) – initial and follow-up surveys
- Comprehensive Score for Financial Toxicity (modified FACIT-COST) – follow-up surveys

- Healthcare Utilization – follow-up surveys (proxy for patient)
- Intervention Assessment – follow-up surveys (intervention arm only); and
- demographic items, including social support and health literacy (single item).

Family of patients who die will receive after-death questionnaires at the usual schedule but at least 4 weeks after the patient's death. The after-death questionnaire contains: decision-making, FACIT-COST, QUAL-E FAMILY (revised), HADS, IES-6, SF-1 and demographic items.

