#### 9.4.3 ANALYSIS OF THE SECONDARY ENDPOINT(S)

- Specific Aim 2, Secondary Endpoints

This aim will include utilization and costs during the study period from the EHR and institutional metrics. Results will be reported as:

- Hospital readmission: 30 days after discharge from the index hospitalization
- Hospital free days: 1 month (30 days) after randomization, 3 months (91 days) after randomization, 6 months (183 days) after randomization
- ICU free days: 1 month (30 days) after randomization, 3 months (91 days) after randomization, 6 months (183 days) after randomization
- Healthcare Costs: from randomization to discharge from index hospitalization, up to 6 months (183 days)
- Healthcare Costs: from randomization to 30 days after randomization

- Specific Aim 3, Other Outcomes

We will perform a thematic analysis of transcribed interviews to explore feedback on the intervention and ways to improve the intervention delivery and implementation. Analyses will be guided by the Consolidated Framework for Implementation Research (CFIR) in exploration of factors effecting implementation and by Outcomes for Implementation Research in exploration of implementation outcomes. Qualitative data will be imported into analytic software, where investigators will perform iterative, inductive coding to identify recurrent themes, categories, and relationships among themes and categories.

---

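### IES-6 is measured only at follow-up, so the own-baseline adjustment in 9.4.2 cannot be applied to it, and the plan names no substitute although baseline HADS-A and HADS-D are held

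*Combined protocol and SAP*

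**What the plan says.** Section 9.4.2 sets out a linear mixed model for HADS depression at 1, 3 and 6 months. On covariates it makes one commitment, "We will also adjust for site, since randomization is stratified by site", and one conditional statement, that the team will "consider adjustment for response (symptoms of depression for primary outcome) at baseline (randomization". It then extends the method: "We will use a similar approach for the other continuous family and patient outcomes". No covariates are named for any particular secondary outcome.

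Section 3 lists post-traumatic stress, measured by IES-6, as a secondary endpoint. The questionnaire schedule in Section 4.1 shows the difference between the two instruments:

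- "Hospital Anxiety and Depression Scale (HADS) – initial and follow-up surveys"
- "Impact Of Events Scale-Revised (IES-6) – follow-up surveys"

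Covariates appear in two other places. Section 5.5 says sex/gender and race/ethnicity will enter the multivariate analyses, without saying which analyses those are. Section 9.4.1 refers to sensitivity analyses adjusted for covariates, without assigning covariates to outcomes. Neither mentions baseline distress as a covariate for IES-6.

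**The concern.** The one outcome-related covariate that 9.4.2 describes is the baseline value of the outcome itself. IES-6 has none, so an analyst following the text has site and no indication of what else to use. A relative's anxiety and depression at enrolment are plausible predictors of later traumatic stress. They are already collected, and Section 9.4.9 already uses HADS at enrolment to define a subgroup.

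Two things are at stake. The first is precision for a secondary outcome to which Section 9.2 assigns no SD and no detectable difference; it offers only a general statement about power for the other continuous outcomes. The second is pre-specification: if the IES-6 covariates are not named in advance, someone will have to choose them later.

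**Working it through.** **Inputs from Section 9.2:** two-sided 5% test, 150 relatives per arm with one per patient, 3 measurements, HADS depression SD 4.2, ICC 0.2.

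**Step 1. Reproduce the plan's figure.** With m visits and n per arm,

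detectable difference = SD × √[(1 + (m − 1) × ICC)/m] × (z₀.₉₇₅ + z_power) × √(2/n).

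At 80% power: 4.2 × √(1.4/3) × (1.960 + 0.842) × √(2/150) = 4.2 × 0.683 × 2.802 × 0.1155 = 0.928, against 0.93 stated. The same formula gives 1.074 at 90% power (stated 1.07), 0.859 at ICC 0.1 (stated 0.86) and 1.052 at ICC 0.4 (stated 1.05). The plan's figures therefore assume no baseline covariate, and leaving one out of the IES-6 model contradicts none of them.

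**Step 2. Add a person-level baseline covariate.** Let r be its correlation with each follow-up score (the multiple correlation if HADS-A and HADS-D enter together). In SD² units, the variance of the three-visit mean falls from (1 + 2 × ICC)/3 to (1 + 2 × ICC)/3 − r².

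Example at ICC 0.2 and r = 0.3: 0.467 − 0.090 = 0.377. The detectable difference falls from √0.467 × 2.802 × 0.1155 = 0.221 SD to √0.377 × 2.802 × 0.1155 = 0.199 SD.

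**Step 3. Range.** The documents give no IES-6 SD, ICC or correlation with HADS. Results are therefore in units of the IES-6 SD, and every r and ICC below is an assumption. Power is 80%, with 150 per arm and 3 visits.

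| Assumed ICC | Unadjusted | r = 0.2 | r = 0.3 | r = 0.4 |
|---|---|---|---|---|
| 0.2 | 0.221 | 0.211 (−4.4%) | 0.199 (−10.2%) | 0.179 (−18.9%) |
| 0.4 | 0.251 | 0.242 (−3.4%) | 0.231 (−7.8%) | 0.215 (−14.4%) |
| 0.6 | 0.277 | 0.269 (−2.8%) | 0.259 (−6.3%) | 0.245 (−11.6%) |

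The reduction runs from about 3% to 19%. Put another way, power at the unadjusted 80% difference rises to between 82% and 93%.

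**Step 4. Limit on r.** In a random-intercept model a person-level covariate can explain only between-person variance, so r² cannot exceed the ICC. At ICC 0.2, r is at most √0.2 = 0.447. The value 0.4 is feasible (0.16 < 0.20); 0.5 is not (0.25 > 0.20). The table stops at 0.4 for that reason.

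**Step 5. Is the baseline HADS score always pre-randomisation?** No. Under Section 8.1, randomisation follows receipt of one relative's completed baseline questionnaire, further relatives may enrol until one month after the patient is randomised, and the facilitator makes contact within one business day of randomisation. A late relative's first HADS score may therefore already reflect the intervention and must not serve as a covariate. The table assumes that every relative has a true pre-randomisation score. The gain shrinks with the share who do not, which the documents do not give.

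**The case against.** The strongest reply is that this is an optional efficiency gain for one secondary outcome. Randomisation protects the comparison without covariates, the trial is sized on HADS depression, and the number to be randomised does not change. All of that stands.

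Four stronger readings are tempting, and the documents do not support them.

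- **That IES-6 is an exception to a firm rule of own-baseline adjustment.** There is no such rule. Section 9.4.2 says only that the adjustment will be considered, even for the primary outcome.
- **That IES-6 receives no prognostic adjustment at all.** Site is in the model, Section 5.5 promises sex/gender and race/ethnicity, Section 9.4.1 plans covariate-adjusted sensitivity analyses, and a similar approach need not be an identical one. What is missing is any named baseline-distress covariate for IES-6.
- **That free days and costs have the same gap**, since they have no baseline value either and Section 4.1 abstracts "data required to calculate APACHE II scores". Section 9.4.3 lists only how these results are to be reported, for example "ICU free days: 1 month (30 days) after randomization", and states no model. There is no covariate set to complete, and the linear-model arithmetic above cannot be carried over to them.
- **That baseline HADS might explain 30% of the variance of a single IES-6 score.** At an ICC of 0.2 that is impossible by Step 4. Any such percentage would have to refer to the three-visit mean.

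One further objection stands in full: adjusting for every score labelled baseline could condition on a variable affected by treatment. The fix has to prevent this.

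**Conclusion.** The point holds as a minor one. The only outcome-related covariate in 9.4.2 is unavailable for IES-6, suitable substitutes are already collected, and the plan does not name them. The consequence is lost precision and an open choice of covariates; it is not bias, and no stated power figure is wrong. The likely size is a detectable difference about 3% to 19% smaller with adjustment. This assumes correlations of 0.2 to 0.4, ICCs of 0.2 to 0.6, 150 relatives per arm, three complete visits, and a pre-randomisation HADS score for every relative. None of the IES-6 quantities can be checked from the documents. If the true correlation is below 0.2, the gain is smaller still.

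**What to change.** Add to Section 9.4.2, before IES-6 is compared between arms:

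> IES-6 will be adjusted for site and for HADS-A and HADS-D measured before randomisation. No HADS score obtained after randomisation will be used as a covariate. For relatives enrolled after randomisation, and any other relative without a pre-randomisation score, the mean of the pre-randomisation values over both arms will be substituted.

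The cost is this short addition to the SAP and one extra handling rule for late-enrolled relatives, which requires comparing each first HADS date with the randomisation date. There is no new data collection, no added burden on relatives and no change to the sample size.
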